***Total time for Completion of above surveys: 20-30 minutes/assessment***

To minimize survey fatigue, only individuals who endorse difficulty with the following items will be asked to complete the questionnaires listed below at each assessment time point.

g. **Anger/Frustration** measured using the LEVEL 2 – Anger – Adult (PROMIS Emotional Distress – Anger - Short Form). This 5-item self-reported survey measures the pure domain of anger over the past 7 days, using a 5-point Likert scale ranging from 1 (never) to 5 (always).

Time for completion: 5 minutes

h. **Pain** using the PROMIS V1.1 - Pain Interference 6a Short Form. This 6-item self-reported survey measures the severity of pain and its impact on a person's ability to function over the past 7 days, using a 5-point Likert scale ranging from 5 (never) to 1 (always).

Time for completion: 5 minutes

i. **Sleep quality** using the LEVEL 2 – Sleep Disturbance – Adult (PROMIS Sleep Disturbance – Short Form). This 7-item self-reported survey measures sleep quality, sleep depth, and restoration, including difficulties with falling asleep or staying asleep and satisfaction with sleep over the past 7 days, using a 5-point Likert scale ranging from 1 (not at all) to 5 (very much).

Time for completion: 5 minutes

***Total time for additional survey completion: 15 minutes/assessment***

**Intervention:**

The specific curriculum/weekly session topics for the 12-week DBT program have been selected from previously developed DBT protocols used in the field by experienced and licensed mental health professionals and co-developed with study team patient partners (Table 1).

Before beginning either the in-person or the virtual program, participants will attend a brief orientation with the DBT clinical psychologist to review the program goals and ask any questions.

We plan to hold the in-person group DBT session first. Participant groups will meet weekly with the DBT therapist for a maximum of 2 hours, including snack or meal and social time. Meetings will be held within the SOGH campus but outside of clinical care areas and away from the hemodialysis unit (in the Chronic Disease Innovation Centre boardroom/SOGH meeting rooms/Wellness Institute meeting rooms depending on availability). Participants will receive reimbursement for transportation to and from sessions to facilitate attendance.

Subsequently we will review feedback from this first in-person group and potentially modify structure/plans for DBT sessions based on participant feedback and discussion with research team and then run the 12-week virtual DBT session. This group will meet weekly for a maximum of 90 minutes virtually through the secure Zoom Healthcare Platform with the clinical psychologist leading the group and one co-facilitator (individual who has a professional healthcare degree e.g. OT, social work, MD, nursing). Each week, participants will be sent an e-mail or text with an invitation link, as per their preference, for the group's Zoom meeting.

Both in-person and virtual DBT group participants will be provided with weekly session reminders and the relevant program materials by the research coordinator. This will include electronic or hardcopies of worksheets and handouts accompanying each week's content and videos that will be delivered by mail/email/drop off in HD unit as per individual preference. The group leader or co-leader may also check in with participants throughout the 12-week program periodically in an individual meeting.

**Table 1: Proposed Weekly Schedule for 12 Week DBT Program Delivery**

Weeks 1-3: Mindfulness (Foundation for All Skills)	
Week 1: Introduction to DBT & Core Mindfulness	Overview of DBT and group expectations
	What is mindfulness? (Wise Mind, Reasonable Mind, Emotion Mind)
	Exercise: "Leaves on a Stream" meditation
	Homework: Mindfulness practice (observe and describe one activity mindfully)
Week 2: Mindfulness – What & How Skills	What Skills: Observe, Describe, Participate
	How Skills: Non-judgmentally, One-mindfully, Effectively
	Exercise: "Five Senses Grounding"
	Homework: Practice a "What" skill daily
Week 3: Practicing Mindfulness in Daily Life	Barriers to mindfulness
	Self-compassion and present-moment awareness
	Exercise: Body scan meditation
	Homework: Daily mindfulness journaling
Weeks 4-6: Distress Tolerance (Coping with Crisis Without Making It Worse)	
	Distraction skills (ACCEPTS: Activities, Contributing, Comparisons, etc.)

Week 4: Crisis Survival Skills – ACCEPTS & TIPP	TIPP (Temperature, Intense Exercise, Paced Breathing, Paired Muscle Relaxation)
	Exercise: Cold water face immersion (TIPP)
	Homework: Try two ACCEPTS skills during distress
Week 5: Reality Acceptance – Radical Acceptance & Willingness	What is radical acceptance? Letting go of suffering
	Turning the mind toward willingness
	Exercise: Half-smile & Willing Hands
	Homework: Notice resistance and practice radical acceptance
Week 6: Self-Soothing & Improving the Moment	Mindfulness of current thoughts
	Self-soothe with the five senses
	IMPROVE skills (Imagery, Meaning, Prayer, Relaxation, etc.)
	Exercise: Create a self-soothe kit
	Homework: Practice self-soothing at least twice this week
Weeks 7-9: Emotion Regulation (Understanding & Managing Emotions)	
Week 7: Understanding Emotions & Checking the Facts	Why we have emotions & how they work
	Checking the facts to reduce emotional intensity
	Exercise: Identify an emotion and fact check it
	Homework: Use "Check the Facts" worksheet on a distressing emotion
Week 8: Opposite Action & Problem-Solving	Opposite action: Changing emotions by acting opposite
	When to problem-solve vs. when to accept
	Exercise: Role-play opposite action for anger
	Homework: Use opposite action in a real-life situation
Week 9: Building a Life Worth Living – ABC PLEASE	Mindfulness Review
	Accumulate positive experiences
	Build mastery & Cope ahead
	PLEASE (Physical health factors affecting emotions)
	Exercise: Create a "build a life worth living" action plan
	Homework: Identify & schedule one positive experience this week
Weeks 10-12: Interpersonal Effectiveness (Building Stronger Relationships)	
Week 10: DEAR MAN – Asking for What You Need	Describe, Express, Assert, Reinforce, Mindful, Appear confident, Negotiate
	Exercise: Role-play using DEAR MAN
	Homework: Use DEAR MAN in a real-life situation
Week 11: GIVE & FAST – Maintaining Relationships & Self-Respect	GIVE (Be Gentle, Interested, Validate, Easy Manner)
	FAST (Be Fair, No Apologies, Stick to Values, Be Truthful)
	Exercise: Practice GIVE & FAST in a conversation

	Homework: Identify an opportunity to use GIVE or FAST
Week 12: Bringing It All Together & Graduation	Review of all DBT skills
	Identifying personal strengths and areas for growth
	Discuss plans for balance/ maintenance
	Exercise: Create a personal DBT plan for ongoing practice
	Homework: Reflect on how DBT has impacted your life

### **Recruitment and Consent for DBT Groups:**

At SOGH, there are currently 160 individuals that start hemodialysis per year. For the purposes of this study, we will aim to recruit 15 individuals, to account for no shows and dropouts, for the in-person DBT group from the SOGH Hemodialysis Units and Multi Care Kidney Clinic. For the virtual DBT group, we will recruit 20 individuals from SOGH and HSC Hemodialysis Units and relevant Kidney Clinics.

Prior to the initiation of the DBT pilot intervention, [name] and the research coordinator will notify and orient healthcare staff to the study through an emailed letter of information and brief presentation to staff in the HD units and Kidney Clinics at both sites. An information poster advertising the DBT groups will be posted in the waiting room of Kidney Clinics and HD waiting rooms at both sites.

Potential recruits for the DBT groups will be screened for eligibility by a member of the individual's circle of care based on the inclusion criteria. If eligible, the individual's bedside or clinic nurse will approach them to briefly introduce the study and offer the potential recruit to opportunity be contacted by the study research coordinator for more information about the study by signing the Consent to Contact Form. This will then be returned to the study research coordinator. Participants will then be contacted by the study research coordinator (in person at hemodialysis/clinic or by phone call or email depending on the individual's preference) who will describe the study, the purpose of the research, the voluntary nature of participation and that participants may withdraw at any point in time and that the decision to participate or not will not impact their standard medical care. The coordinator will review the written consent form for the DBT intervention project with potential participants. Potential participants will be offered the opportunity to ask their own questions and request additional information about the study and will be given at least 24 hours to consider whether they want to participate or not. Consent to participate will be indicated through an individual's signature on the written consent form. All participants will read, sign, and date the consent form before undergoing any study procedures. A copy of the signed consent will be given to the participant. All original signed consents will be filed in a locked cabinet at CDIC.

### **DBT Data Collection:**

Demographic and clinical data will be collected at time of consent directly from participant and medical chart review. Data collected will include CKD diagnosis date, dialysis status (planned HD start date, HD start date, HD shift and days), comorbidities, age, gender, ethnicity, employment status, highest level of education, approximate annual income, and marital status. Clinical data collected at baseline and Week 12 (study end) from hemodialysis chart will include dialysis clearance (Kt/V), medications, mean weekly

interdialytic fluid gains (in week before baseline assessment), and laboratory data. The blood work result for hemoglobin, albumin, potassium, calcium, phosphate, and parathyroid hormone taken at the closest time point to the study visit will be transcribed to CRF forms from the HD chart. Monthly blood work samples are taken every 4-6 weeks pre-dialysis on a mid-week dialysis day routinely as standard of care in in-centre hemodialysis. Hardcopy print out of results is placed in the hemodialysis chart as routine standard of care.

Study outcome assessments will occur at baseline, 6-weeks and following the 12-week DBT intervention (within +/- 10 days of this timepoint). Surveys will be distributed by the research coordinator and administered by hardcopy or electronically through participant's personal email (as per participant preference) and will be de-identified using each participant's unique study identifier. See Table 2.

### **DBT Statistical Analysis:**

Descriptive quantitative analyses (counts, proportions) will assess feasibility outcomes. Baseline survey scores will be reported as median (interquartile range) and proportion of answers for each question on survey in each Likert scale category. Change in survey scores over time will be reported as median (interquartile range). Aggregate changes in scores of each survey between assessment timepoints will be compared using Mann-Whitney U test and Chi-square test as appropriate. Due to small sample size and exploratory nature of the study, statistically significant changes in secondary outcomes are not anticipated. However, P-value of < 0.05 will be considered statistically significant. All data analysis will be completed in SAS 9.5 (Carey,NC).

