### **Dialectical Behavioural Therapy**

Based on data gathered through the Mind the Gap surveys and the Priority Setting Workshop, we have identified the top 5 challenges to mental well-being in facility-based hemodialysis as: loss of control, lack of acceptance and/or adjustment to the situation, lack of trust and confidence in the healthcare system and providers, dialysis-related symptoms, and feeling overwhelmed. After discussions with various stakeholders, we reached consensus that implementation of a Dialectical Behavioural Therapy (DBT) program, which targets 4 key concepts: mindfulness, distress tolerance, emotional regulation, and interpersonal effectiveness, has potential to address most of these five challenges. DBT has been used in many different settings (treatment of borderline personality disorder, substance abuse, improving self-esteem in adolescents, improving corporate culture) and populations, but to our knowledge has not been studied in the hemodialysis population.

We will use a quasi-experimental pre/post study design to pilot two 12-week group DBT sessions in Manitoba that will be led by a licensed clinical psychologist who is trained and certified in delivery of DBT. Licensed clinical psychologist services will be provided by Tomfohr&Roos. Additional staff (e.g. Licensed Kidney Health Manitoba Social Worker at SOGH and/or a clinical psychology practicum student supervised by the licensed psychologist) may also co-facilitate the group depending on timing and human resources availability. An initial DBT group will meet in person at SOGH weekly for 12 weeks. Following completion of and incorporating feedback from the first session, a second virtual 12-week DBT group session will be implemented.

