**Outcomes:*****Primary Outcome Feasibility measured by (collected at end of 12-week DBT session):***

a. *Recruitment:* Number of individuals recruited/Number of eligible individuals approached  $\geq$  30%

b. *Attendance:*

i. Mean Proportion of total DBT sessions attended  $\geq$  50%

- ii. Proportion of participants who attend all DBT sessions and complete all weekly homework sheets

*c. Study withdrawal:*

- i. Proportion of individuals who miss  $\geq 4$  DBT sessions in a row
- ii. Proportion of and reasons for study withdrawal

*d. Difference in recruitment and attendance rates between in-person and virtual DBT sessions*

**Secondary Outcomes:** measured by median change from pre-, to 6 weeks, and post-intervention (12 weeks):

All participants will complete:

a. **Anxiety symptoms** measured by the LEVEL 2 – Anxiety – Adult (PROMIS Emotional Distress – Anxiety - Short Form). This 7-item self-reported survey asks about the current severity/presence of the individual's anxiety over the past 7 days, using a 5-point Likert scale ranging from 1 (never) to 5 (always).

Time for completion: 5 minutes

b. **Resilience** measured using the two-item version of the Connor–Davidson Resilience Scale. This 2-item self-reported survey asks the individual to respond to the following statements: "I am able to adapt when changes occur" and "I tend to bounce back after illness, injury, or other hardships" using a 5-point Likert scale ranging from 0 (not true at all) to 4 (true nearly all of the time). Validated in multiple populations.

Time for completion: Less than 5 minutes

c. **Dialysis-related symptoms** using the Edmonton Symptom Assessment System Revised (ESAS-r). This 10-item self-reported survey asks about the current severity/presence of common symptoms experienced by people receiving hemodialysis over the past 7 days, using an 11-point Likert scale ranging from 0 to 10 (i.e.; for pain: 0 = no pain at all; 10 = worst pain possible).

Time for completion: 5 minutes

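### Survey scores from the same participants are compared between timepoints with independent-samples tests, so the exploratory secondary P-values are probably too large

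*Protocol*

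**What the plan says.** The Protocol's Dialectical Behavioural Therapy section sets the design: "We will use a quasi-experimental pre/post study design to pilot two 12-week group DBT sessions in Manitoba". There is no control arm. On timing, DBT Data Collection says: "Study outcome assessments will occur at baseline, 6-weeks and following the 12-week DBT intervention". It adds that the surveys "will be de-identified using each participant's unique study identifier", so each person's scores can be linked over time. The Outcomes section defines the secondary outcomes as median change across the three assessments, and Table 2 shows the same instruments at all three visits.

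For the comparison itself, DBT Statistical Analysis says: "Aggregate changes in scores of each survey between assessment timepoints will be compared using Mann-Whitney U test and Chi-square test as appropriate". It then sets a threshold: "P-value of < 0.05 will be considered statistically significant". The same paragraph calls the study exploratory and does not expect significant secondary changes. The Protocol names no paired or repeated-measures test for these surveys.

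**The concern.** Mann-Whitney U and the ordinary Chi-square test take the two sets of observations as coming from different, unrelated people. Here they come from the same people. When a person's scores are positively correlated, the change varies less than a difference between two independent groups would. An unpaired test uses the larger variance, so its P-values are too large and it misses real change more often than it should.

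This is not a detail left to a statistical analysis plan. The Protocol names specific tests for a specific comparison. An analysis plan that followed it would inherit the problem, and one that did not would contradict it. The P-values would also not belong to the Protocol's own summary, which is the change within participants. In a small uncontrolled pilot, pairing is an important source of precision.

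**Working it through.** The Protocol gives no power or sample-size calculation for the secondary outcomes, so there is no figure to reproduce. The check is whether the named tests hold the stated 0.05 level on paired data.

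**Inputs from the Protocol.** Threshold 0.05. Sidedness is not stated, so two-sided is assumed. Recruitment and Consent for DBT Groups gives the targets: "we will aim to recruit 15 individuals, to account for no shows and dropouts, for the in-person DBT group" and "For the virtual DBT group, we will recruit 20 individuals from SOGH and HSC Hemodialysis Units". That is 15 and 20, or 15 + 20 = 35 if pooled.

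**Assumptions.** The within-person correlation ρ (range 0.3 to 0.7) and a 0.5 SD change; the Protocol gives neither.

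**Step 1: large-sample formula.** With equal variances σ², the difference between two means on the same n people has variance 2σ²(1−ρ)/n. An unpaired test uses 2σ²/n. Its z statistic therefore has null standard deviation √(1−ρ), and its true size is 2[1 − Φ(1.96/√(1−ρ))].

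- ρ = 0: 1.96/1 = 1.96, size 5.0%
- ρ = 0.3: 1.96/0.837 = 2.34, size 1.9%
- ρ = 0.5: 1.96/0.707 = 2.77, size 0.56%
- ρ = 0.7: 1.96/0.548 = 3.58, size 0.03%

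Power at n=35 and ρ = 0.5, in SD units: the true standard error is √(2×0.5/35) = 0.169. The unpaired critical difference is 1.96×√(2/35) = 0.469. Unpaired power is Φ((0.5−0.469)/0.169) = 57%. Paired power is Φ(0.5/0.169−1.96) = 84%.

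**Step 2: simulation of the rank tests.** 4,000 runs per scenario, two timepoints, normal scores rounded to a 7 to 35 scale (7 items scored 1 to 5; mean 20 and SD 6 assumed). The Monte Carlo standard error is √(0.05×0.95/4000) = 0.3 points near 5% and √(0.5×0.5/4000) = 0.8 points near 50%.

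| n | ρ | Size, Mann-Whitney | Size, signed-rank | Power, Mann-Whitney | Power, signed-rank |
|---|---|---|---|---|---|
| 15 | 0.3 | 2.5% | 5.6% | 20.7% | 31.7% |
| 15 | 0.5 | 0.9% | 5.1% | 18.1% | 42.3% |
| 15 | 0.7 | 0.2% | 4.5% | 14.5% | 62.3% |
| 20 | 0.3 | 2.4% | 5.3% | 29.4% | 42.5% |
| 20 | 0.5 | 0.7% | 4.6% | 26.9% | 55.6% |
| 20 | 0.7 | 0.2% | 5.8% | 23.9% | 76.5% |
| 35 | 0.3 | 2.3% | 5.3% | 51.8% | 65.2% |
| 35 | 0.5 | 0.8% | 5.3% | 52.5% | 79.9% |
| 35 | 0.7 | 0.2% | 5.1% | 53.6% | 95.1% |

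At ρ = 0 the Mann-Whitney size is 3.9% at n=15 and 5.0% at n=20 and n=35, so it is close to nominal only when repeated scores are uncorrelated.

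**Step 3: Chi-square.** The same scores were split at 20 (an assumed cut) and tested without continuity correction. At n=35 the size is 2.4%, 1.4% and 0.5% for ρ = 0.3, 0.5 and 0.7. Exact McNemar gives 2.6%, 2.4% and 2.0%. Power at n=35 is 34.0%, 33.5% and 31.1% for Chi-square against 33.4%, 39.2% and 46.3% for exact McNemar. At n=15 exact McNemar is itself conservative (size 0.4% to 1.6%) and has no power advantage (8.1% to 9.5%, against 10.8% to 15.7%). For binary responses the case for McNemar is that it matches the design; it does not rescue power in the smaller group.

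**The case against.** **Could the sentence be read so that the tests are right?** Mann-Whitney on change scores would be valid for in-person against virtual participants. But the sentence speaks of timepoints, and the only contrast of the two formats under Outcomes concerns recruitment and attendance. The words on appropriateness choose between two tests that both need independence.

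**Does it matter?** Much of this objection stands. The primary outcome is feasibility, described by counts and proportions. The focus groups depend on feasibility, not on any secondary P-value. The secondary tests are exploratory, and with positive correlation the error produces no false claim of benefit.

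Several stronger inferences are tempting, and the Protocol does not support them:

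- **That every secondary P-value is wrong, or that false positives are inflated.** The miscalibration depends on an unstated correlation and vanishes at zero. With positive correlation it runs in the conservative direction. Only the timepoint comparisons are affected.
- **That most of the information is lost.** At n=35 and ρ = 0.3 the power gap is 51.8% against 65.2%.
- **That the expectation of no significant change is an artefact of the test.** The Protocol attributes it to small sample size and exploratory purpose, and no calculation ties it to the test. Even signed-rank reaches only 42.3% at n=15 and ρ = 0.5.
- **That Chi-square would be run on sparse five-category tables.** The Protocol does not say so. It specifies category proportions for baseline reporting, and two instruments use 0 to 10 scales.

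The sample sizes are also best case. The 15 already allows for dropout, and pooling to 35 is not stated. With an assumed 10 completers, simulated signed-rank power is about 28% at ρ = 0.5 and 44% at ρ = 0.7.

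**Conclusion.** The point holds, at moderate severity: the Protocol applies independent-samples tests to repeated measurements on the same identified people. For an assumed correlation of 0.3 to 0.7 the P-values comparing timepoints are too large. The cost is lost power, modest at the low end of that range and substantial at the high end. These figures rest on two-sided testing, normal-type scores, a 0.5 SD change and full retention, none of which the Protocol fixes. A practical consequence is that a real change in, say, anxiety or distress could be reported as null and mislead later planning. The feasibility outcomes, medians, interquartile ranges, proportions and the single-time end-of-study questionnaire are unaffected.

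**What to change.** In DBT Statistical Analysis, replace the named tests with paired ones:

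- **Scores:** Wilcoxon signed-rank on within-participant change from baseline to 6 weeks and to 12 weeks, or a Friedman test or mixed model across the three times. Report the median change with a 95% confidence interval.
- **Paired binary responses:** McNemar.
- **Anger, pain and sleep forms:** these go only to people who endorse difficulty at each time point, so pairs may be incomplete. Analyse participants with both assessments and report the number of pairs. Someone who improves enough to stop endorsing the problem may drop out of the pairs, so that number is needed to read the result.
- **Mann-Whitney:** keep it only for any comparison of change scores between the in-person and virtual groups.

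The essential change is from unpaired to paired; the choice among paired methods is open. It costs a few sentences and needs no new data, visits or participants.
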